2.8.1.4 Progression-free survival

Progression-free survival is defined as the time from the date of first dose of study treatment to the date of the first documented progression or death due to any cause. PFS will be evaluated based on Investigator or BIRC assessment according to RECIST 1.1.

PFS will be censored if no PFS event (radiological progression or death) is observed prior to the first to occur between: (i) the analysis cut-off date, and (ii) the date when a new anti-neoplastic therapy (with the exception of protocol-allowed radiotherapy) is started. The censoring date will be the date of the last adequate tumor assessment prior to cut-off/start of new anti-neoplastic therapy.

Clinical deterioration will not be considered as documented disease progression. A PFS event date will be included in the analysis if it occurs after one missing tumor assessment. If the PFS event is observed after two or more consecutive missing tumor assessments, PFS will be censored at the last adequate tumor assessment prior to the first missing assessment.

The date of last adequate tumor assessment is the date of the last tumor assessment with overall lesion response of CR, PR, SD, or non-CR/non-PD before an event or a censoring reason occurred. In this case the last tumor evaluation date at that assessment will be used. Participants without a post-baseline tumor assessment will be censored at the date of first dose of study treatment.

A missing adequate tumor assessment is defined as a tumor assessment (TA) not performed or a tumor assessment with overall lesion response of “not evaluable (NE)”. The rule to determine the number of missing TAs is based on the time interval between the date of last adequate tumor assessment and the date of an event. Details are described in [Section 4.5](#).

[Table 2-5](#) shows the censoring and event date options and the outcomes for PFS. Details about censoring rules for PFS follow the RECIST 1.1 guidelines ([\[Study Protocol Section 10.8\]](#)) and are provided in [Section 4.5](#).

The distribution of PFS will be estimated using the Kaplan-Meier method, and the Kaplan-Meier curve, median, and 95% CI of the median will be presented by cohort.

A subgroup analysis of PFS will be prepared for cohort A for the subgroups 4a to 4h.

Censoring pattern for PFS

The number of participants censored and the reasons for censoring will be summarized using descriptive statistics and presented separately for Investigator assessment and BIRC assessment.

Concordance analysis of PFS

A cross-tabulation of PFS by BIRC assessment vs. PFS by Investigator assessment by PFS event type (i.e., “death”, “PD”, “censored” for each of the two sources) will be prepared to investigate the discordance between the two sources. The discordance rate (in %) between BIRC and Investigator assessment will be summarized.

A summary table will be produced displaying the PFS timings for the Investigators’ assessment compared to the BIRC assessment. For progression assessments, the frequency and percent of participants with complete agreement (occurring on the same date plus or minus 7 days of each other), progression later, progression earlier, and cases where progression was called by one method and censored by the other will be displayed. Similarly, if censoring was recorded, the frequency and percent of participants with complete agreement, censoring called later, censoring called earlier, and cases where censoring was called by one method and progression was called by the other method will be displayed.

2.8.1.5 Overall survival

Overall survival is defined as the time from the date of first dose of study treatment to the date of death due to any cause. If a participant is not known to have died, then OS will be censored at the latest date the participant was known to be alive (on or before the analysis cut-off date). The OS distribution will be estimated using the Kaplan-Meier method, and the Kaplan-Meier curves, medians and 95% confidence intervals of the medians will be presented for each cohort. The OS data will also be listed.

Censoring pattern for OS

The number of participants censored for the OS analysis will be summarized. In addition, a summary of the reasons for OS censoring (“Alive” or “Lost to follow-up”) will be provided.

2.8.2 Analyses for the STK11 pooled group

Participants in the FAS pooled from cohort A and cohort B, whose tumors harbor an STK11 mutation, regardless of PD-L1 expression status, will form the STK11 pooled group (subgroup 1 in [Section 2.2.1](#)).

The endpoints for the subgroup are ORR, DOR, DCR, TTR, and PFS by BIRC and Investigator assessment as well as OS. The analysis will follow the same specifications as in [Section 2.7](#).

2.8.3 Listings

Listings for the efficacy endpoints will be provided by cohort and separately for the STK11 pooled group.

2.9 Analyses supporting secondary objectives – safety

For all safety analyses, the safety set will be used. All listings and tables will be presented by cohort.

Safety summaries (tables, figures) include only data from the on-treatment period as defined in [Section 2.1.3.8](#), with the exception of baseline data which will also be summarized where appropriate (e.g., change from baseline summaries). In particular, summary tables for adverse events (AEs) will summarize only on-treatment events, with a start date during the on-treatment period (treatment-emergent AEs). In addition, a separate summary for deaths including on-treatment and post-treatment deaths will be provided.

All safety data, regardless of observation period, will be listed and assessments collected in the post-treatment period will be flagged in the listings.

2.9.1 Adverse events (AEs)

2.9.1.1 General rules for AE reporting

Adverse events which will be counted in summary tables are those that are treatment-emergent. These events have an onset on or after the start of the on-treatment period, or which were present prior to the start of the on-treatment period but increased in severity, changed from being not suspected to being suspected of study drug relationship, or developed into SAEs after the start of the on-treatment period.

2.9.1.2 AE analyses

Summary tables for AEs will include only the treatment-emergent events. AEs will be summarized by system organ class and/or preferred term, and severity (based on CTCAE version 5.0). Separate summaries will be provided for study treatment related treatment-emergent AEs, all deaths, on-treatment deaths, all serious adverse events and treatment-related SAEs, other significant AEs, treatment-related AEs leading to treatment discontinuation, dose adjustment, and additional therapy.

All AEs, deaths, and serious adverse events (including those from the pre- and post-treatment periods) will be listed and those collected during the post-treatment period will be flagged. A listing of AE MedDRA coding will be generated to provide the list of preferred terms that changed as a result of the re-mapping process to the latest MedDRA version.

A participant with multiple adverse events within a SOC will only be counted once towards the total of the system organ class. A participant with multiple occurrences of an AE will be counted only once in the respective AE category. A participant with multiple CTCAE grades for the same PT will be summarized under the maximum CTCAE grade recorded for the event. AEs with missing CTCAE grade will be included in the “All grades” column of the summary tables by grade and will be counted in both ‘missing grade’ and available maximum

grade in the summary tables by maximum grade. An AE with missing seriousness will be counted as non-serious AE.

In AE summaries, the SOC will be presented alphabetically, and the PT will be sorted within SOC in descending frequency. Summaries by CTCAE grade will present columns for grades 3/4, grade 5, and all grades, as applicable.

In summary, the following AE summaries will be generated:

- AEs regardless of study treatment relationship
- AEs suspected to be study treatment related
- On-treatment deaths, by SOC and preferred term
- All deaths, by SOC and preferred term
- SAEs regardless of study treatment relationship
- SAEs suspected to be study treatment related
- AEs leading to permanent discontinuation of study treatment regardless of study treatment relationship
- AEs leading to permanent discontinuation of study treatment suspected to be study treatment related
- AEs requiring dose adjustment and/or study treatment interruption regardless of study treatment relationship
- AEs requiring dose adjustment and/or study treatment interruption suspected to be study treatment related
- AEs requiring significant additional therapy regardless of study treatment relationship
- AEs requiring significant additional therapy suspected to be study treatment related
- AEs excluding SAEs regardless of study treatment relationship

2.9.1.3 Clinical trial safety disclosure

For the legal requirements of ClinicalTrials.gov and EudraCT, two tables will be provided by SOC and PT based on the safety set:

- On-treatment AEs which are not SAEs with an incidence greater than 5%
- On-treatment SAEs and SAEs suspected to be related to study treatment

If for the same participant, several consecutive AEs (irrespective of study treatment causality, seriousness, and severity) occurred with the same SOC and PT,

- a single occurrence will be counted if there is ≤ 1 day gap between the end date of the preceding AE and the start date of the consecutive AE,
- more than one occurrence will be counted if there is > 1 day gap between the end date of the preceding AE and the start date of the consecutive AE.

For occurrence, the presence of at least one SAE/SAE suspected to be related to study treatment/non-SAE has to be checked in a block, e.g., among AEs in a ≤ 1 day gap block, if at least one SAE is occurring, then one occurrence is calculated for that SAE.

The number of deaths resulting from SAEs suspected to be related to study treatment and SAEs irrespective of study treatment relationship will be provided by SOC and PT.

2.9.1.4 Adverse events of special interest / grouping of AEs

An adverse event of special interest (AESI) is a grouping of adverse events that are of scientific and medical concern specific to JDQ443. These groupings are defined using MedDRA terms, SMQs (standardized MedDRA queries), high level group terms, high level terms, and PTs (preferred terms). Customized SMQs (Novartis MedDRA queries, NMQ) may also be used. An NMQ is a customized group of search terms which defines a medical concept for which there is no official SMQ available or the available SMQ does not completely fit the need. It may include a combination of single terms and/or an existing SMQ, narrow or broad.

All AESI definitions or AE groupings are specified in the electronic Case Retrieval Strategy (eCRS) in which they are identified by the flag "SP". The latest version of the eCRS available at the time of the analysis will be used.

For each specified AESI, the number and percentage of participants with at least one event of the AESI occurring during the on-treatment period will be summarized. The summaries will present grade, SAE, relationship to study treatment, leading to treatment discontinuation, leading to dose adjustment/interruption, hospitalization, death etc. A listing of the MedDRA terms that define the AESIs will be generated.

Analysis of time to first occurrence of AESI (any grade and grade ≥ 3) will be applied using the Kaplan-Meier method. Duration of first occurrence of AESI (any grade and grade ≥ 3) will also be summarized. These analyses will be performed for AESI regardless of study drug relationship and for AESI suspected to be study drug related. In the absence of an event during the on-treatment period, the censoring date applied will be the earliest of the following dates: date of death, start date of new antineoplastic therapy before experiencing an event, end date of on-treatment period, analysis cut-off date, withdrawal of informed consent date.

All participants who experienced at least one AESI in the Safety set will be included in time to first occurrence of AESI (any grade and grade ≥ 3) and duration of first occurrence of an AESI calculation.

Duration of first occurrence of an AESI (any grade and grade ≥ 3) will be presented for the subset of subjects in the safety set who experienced the event. If there is no resolution during the on-treatment period, a patient will be censored at the earliest of the following dates: death date, new anti-neoplastic antineoplastic therapy start date, end date of on-treatment period, analysis cut-off date, and withdrawal of informed consent date.

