2.1.3.8 On-treatment assessment/event and observation periods

For adverse event reporting the overall observation period will be divided into three mutually exclusive segments:

1. ***pre-treatment period:*** from day of participants informed consent to the day before first administration of study treatment

2. **on-treatment period:** from date of first administration of study treatment to 30 days after date of last actual administration of study treatment (including start and stop date)
3. **post-treatment period:** starting at day 31 after last administration of study treatment.

Safety summaries (tables, figures) and summaries of on-treatment deaths include only data from the on-treatment period with the exception of baseline data which will also be summarized where appropriate (e.g. change from baseline summaries). In addition, all deaths which occurred during the study (i.e. during the on-treatment, and post-treatment periods) will be summarized.

An on-treatment adverse event (or treatment-emergent AE) is defined as any adverse event reported in the on-treatment period.

An on-treatment assessment is defined as any assessment performed during the on-treatment period.

In case at the time of the analysis, the date of last administration of study treatment is missing, on-treatment adverse events/assessments include any adverse event/assessment recorded in the database and which occur after the start date of the study treatment.

Data listings will include all assessments/events, flagging those which were collected during the pre-treatment and post-treatment period.

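### Kaplan-Meier for time to first AESI treats competing events as censoring, and its population sentence contradicts its censoring rule

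*SAP*

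**What the plan says.** SAP 2.9.1.4 states: "Analysis of time to first occurrence of AESI (any grade and grade ≥ 3) will be applied using the Kaplan-Meier method". If there is no event in the on-treatment period, "the censoring date applied will be the earliest of the following dates: date of death, start date of new antineoplastic therapy", and the list continues with "end date of on-treatment period, analysis cut-off date, withdrawal of informed consent date".

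SAP 2.1.3.8 defines the on-treatment period as running "from date of first administration of study treatment to 30 days after date of last actual administration of study treatment". It adds: "An on-treatment adverse event (or treatment-emergent AE) is defined as any adverse event reported in the on-treatment period".

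Two further statements in SAP 2.9.1.4 matter:

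- For each AESI, "the number and percentage of participants with at least one event of the AESI occurring during the on-treatment period will be summarized". This is a crude count and percentage. Protocol 9.4.2.1 plans the same and has no Kaplan-Meier analysis of AESIs.
- On the population: "All participants who experienced at least one AESI in the Safety set will be included in time to first occurrence of AESI". The sentence applies equally to the analysis of AESI duration.

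Neither document plans a competing-risk method. The Kaplan-Meier specification in SAP 4.4.2 names DOR, PFS and OS, not AESIs.

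**The concern.** The censoring rule and the crude summary both frame the event as an AESI in the on-treatment period. Data collection fits that framing. Under the assessment schedule in Protocol 1.3, routine AE reporting stops 30 days after the last dose, and after a new antineoplastic therapy only AEs suspected to be treatment-related are reported.

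For that target, a participant who has died, or whose on-treatment period has ended after permanent discontinuation, can no longer contribute an event. Kaplan-Meier treats these participants as if they remained at the same future risk as those still observed. The onset curve is the only planned AESI display that accounts for time, and it is naturally read as the probability of an AESI by a given month. It would then disagree with the crude percentage in the same report. Characterising safety is a secondary objective.

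The population sentence is a second defect in the same section. A rule for censoring participants without an event has almost nothing to act on if only participants with an event are included.

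**Working it through.** The documents give no AESI rate and no value of the curve, so there is no planned figure to reproduce. The check has three parts.

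**1. Direction (no rates needed).** At each AESI time, Aalen-Johansen adds (probability of being free of AESI and of competing events) × (AESI hazard). The 1-KM curve adds (probability of being free of AESI alone) × (the same hazard). The first probability is never larger than the second and is smaller once a competing event has occurred. So 1-KM is never below the on-treatment cumulative incidence, and it exceeds it from the first AESI after a competing event.

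**2. Size (assumed rates).** Constant hazards: λ1 for AESI, λ2 for death, new therapy or end of the on-treatment period.

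- 1-KM(t) = 1 − exp(−λ1·t)
- Cumulative incidence(t) = λ1/(λ1+λ2) × [1 − exp(−(λ1+λ2)·t)]

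Inputs:

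- λ1: assumed, set so that 1-KM at 6 months is 5%, 10%, 20% or 40%.
- λ2 = ln 2 / median, with proxy medians only. 6.3 and 12.5 months are the PFS and OS of another KRAS G12C inhibitor in pretreated patients (Protocol 2.2.3). 3.7 months is 15.9 weeks × 7 / 30.4375, the median exposure in the first-in-human study (Protocol 2.2.3.3.1), with most patients still on treatment.

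Worked case: λ1 = −ln(0.90)/6 = 0.01756 and λ2 = ln 2/6.3 = 0.1100 per month. At 12 months, 1-KM = 1 − 0.90² = 19.0%. Cumulative incidence = 0.01756/0.1276 × (1 − exp(−1.531)) = 0.1376 × 0.784 = 10.8%.

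At 12 months:

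| 1-KM | Cumulative incidence, median 12.5 months | Median 6.3 months | Median 3.7 months |
|---|---|---|---|
| 9.8% | 7.2% | 5.5% | 3.9% |
| 19.0% | 14.0% | 10.8% | 7.8% |
| 36.0% | 26.9% | 20.9% | 15.4% |
| 64.0% | 49.4% | 39.4% | 30.1% |

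The ratio of 1-KM to cumulative incidence runs from about 1.3 (64.0/49.4) to 2.5 (9.8/3.9). At 6 months with a median of 6.3 months the pairs are closer: 5.0% and 3.7%, 10.0% and 7.4%, 20.0% and 14.8%, 40.0% and 30.1%.

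A simulation (1,000 runs, N = 90, competing median 6.3 months, cut-off uniform between 5.5 and 18 months) compares the curve with the planned crude percentage:

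| Crude share | 1-KM at 12 months | Aalen-Johansen at 12 months |
|---|---|---|
| 10.3% | 18.8% | 10.7% |
| 20.1% | 35.8% | 20.8% |
| 37.9% | 64.3% | 39.4% |

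Aalen-Johansen stays close to the crude share; 1-KM does not.

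**3. The population sentence.** If every included participant has the analysed event, the product-limit estimate ends at zero and 1-KM ends at 100% whatever the true rate. Restricting the same simulation to participants with an event gave 100% in every scenario. Censoring would act only at the margins, for example on participants with a low-grade AESI in the grade ≥ 3 analysis, or with an AESI whose onset was outside the on-treatment period. Even then the denominator is not the Safety Set.

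**The case against.** The strongest objection is that no misleading figure is planned. The SAP does not say that 1-KM will be reported as the share of participants with an AESI. It gives that share as a crude number and percentage, which the simulation shows to be free of this bias. That stands. A reader might infer that the reported AESI incidence itself will be inflated, and the documents do not support this. The problem is confined to the onset curve and to anyone reading it as a probability.

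A reader might also infer that an AESI cannot, by definition, occur after treatment. SAP 2.9.1.4 defines AESIs by MedDRA grouping with no time limit, and later events are still listed and flagged. Ending the on-treatment period makes an event uncounted, not impossible. Only death is a competing event under any target. If the target were risk had treatment continued, the other end points could be treated as censoring, and the direction of bias would depend on whether that censoring is informative. The SAP does not name its target, but its wording points to on-treatment risk. Nor does censoring fall when treatment stops: it falls up to 30 days later.

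The sizes are open to challenge, and fairly:

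- The competing medians are proxies. Here treatment is first-line, may continue beyond progression, and the window adds 30 days, so the slower case may be nearer.
- The cut-off requires only about 24 weeks of assessments, so the smaller 6-month gap may matter more than the 12-month one.
- Without an AESI rate, it cannot be said that competing events will outnumber AESIs.
- Safety is also presented by cohort. In a simulated case with N = 120 (1-KM 21.3%, cumulative incidence 12.2%), the gap of about 9 points compared with a standard error of 6.3 points. With 30 participants the standard error is about 6.3 × √(120/30) = 12.6 points, so in cohort B the gap would be about 0.7 standard errors.

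**Conclusion.** The point holds for on-treatment AESI risk in the full Safety Set: death and the end of the on-treatment period after permanent discontinuation are competing events, and treating them as censoring makes 1-KM too high. The direction does not depend on assumed rates; the size does. For an assumed 12-month 1-KM of 19.0%, cumulative incidence is between 7.8% and 14.0% over the range of competing medians examined, and 10.8% at 6.3 months. At 6 months the last case is 10.0% against 7.4%.

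The population sentence contradicts the censoring rule and must be settled first, because followed literally it swamps the competing-risk effect. Correcting it alone would leave that effect in place, so both changes are needed.

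This is a descriptive, untested analysis with no bearing on ORR or on the crude AESI tables. Priority: minor to moderate.

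**What to change.** In SAP 2.9.1.4:

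1. Include all Safety Set participants in the time-to-first-AESI analysis. Keep the restriction to participants with an event for the duration analysis only.
2. State that the target is the risk of a first AESI in the on-treatment period.
3. Replace Kaplan-Meier with the Aalen-Johansen cumulative incidence of first AESI. Treat death, new antineoplastic therapy, and end of the on-treatment period after permanent discontinuation as competing events.
4. Censor at consent withdrawal, and at the cut-off for anyone still within the on-treatment period, including participants off drug for less than 30 days.

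Because new therapy can start within the 30 days, the text should note that the crude percentage may include a few AESIs with onset after that start which the curve does not count.

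The cost is one PROC LIFETEST option (eventcode=) and a few lines of SAP text; no new data are needed. The downside is that the figure becomes less comparable with Kaplan-Meier AESI plots from other studies.

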8.5.3 Electrocardiograms

Electrocardiograms (ECGs) will be centrally evaluated and must be recorded after 10 minutes rest in the supine position to ensure a stable baseline. The preferred sequence of cardiovascular data collection during study visits is ECG collection first, followed by vital signs, blood sampling, and any remaining assessments for that visit.

The Fridericia QT correction formula (QTcF) must be used for clinical decisions, e.g., at Screening to assess eligibility. The Investigator must calculate corrected QT interval (QTc) if it is not auto-calculated by the ECG machine.

ECGs will be performed at screening, C1D1, C1D15 and at EOT (Table 8-4).

Triplicate 12 lead ECGs are to be recorded approximately 2 minutes apart. The mean QTc value for each visit will be calculated from the triplicate ECGs for each participant.

Table 8-4 Central ECG collection plan

Cycle	Day	Time	ECG Type
Screening		Anytime (before C1D1)	12 Lead, triplicate
1	1	Pre-dose and 4 hours post-dose (within 15 minutes prior to PK)	12 Lead, triplicate
1	15	Pre-dose and 4 hours post-dose (within 15 minutes prior to PK)	12 Lead, triplicate
EOT		Anytime	12 Lead, triplicate
Unscheduled	or Unplanned ECG	Anytime if clinically indicated	12 Lead, triplicate

In order to enable ECG evaluation by the central ECG laboratory for eligibility assessment, ECGs should be submitted to the central ECG laboratory prior to enrollment (to refer to the ECG manual for the turn around time).

In the event that a QTcF value of > 500 ms is observed or if an unscheduled ECG is performed for safety reasons, it is recommended to collect a time-matched PK sample and record the time

and date of the last study treatment intake to determine the drug exposure. Dose adjustments in case of QT prolongation should be performed per Section 6.5.

In the event that a clinically significant ECG abnormality is identified at the site (e.g., severe arrhythmia, conduction abnormality of QTcF > 500 ms), a copy of the assessment is sent to the central ECG laboratory for expedited review and the ECG is repeated at the site to confirm the diagnosis. If the participant is hemodynamically compromised, the Investigator or a medically qualified person must initiate appropriate safety procedures without delay (for example cardioversion).

All ECGs, including unscheduled safety ECGs with clinically relevant findings collected during the study need to be transmitted to the central ECG laboratory for review.

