2.1.3.7 Baseline

For safety and efficacy evaluations, the last available assessment on or before the date of start of study treatment is defined as “baseline” assessment.

If labs with duplicate laboratory measurements taken at the last assessment date on or before the start date of study treatment, then the rule described below will be applied for the calculation of baseline.

If values are from central and local laboratories, the value from central assessment should be considered as baseline.

For gradable labs:

- The value of lower CTCAE grade will be considered as the baseline value.
- If several records have the same absolute grade, but in different directions, two baselines should be created, the record with grade below 0 should be the baseline of the 'Hypo' parameter, and the other record should be the baseline for the 'Hyper' parameters.

For non-gradable labs:

- If both within normal range: take average value
- If one within normal range and the other outside: take the one within normal range
- If both outside normal range: take the one closest to the normal range

If participants have no value as defined above, the baseline result will be missing.

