2.9.4 Other safety data

2.9.4.1 ECG and cardiac imaging data

12-lead ECGs including PR, QRS, QT and QTcF intervals and heart rate will be obtained for each participant during the study. ECG data will be read and interpreted centrally. The average of the ECG parameters at each assessment should be used in the analyses. ECGs collected during the on-treatment period will be summarized.

The number and percentage of participants with notable ECG values will be presented by treatment arm based on the categories below. ECG shift table based on notable values will also be presented by treatment arm.

- QT and QTcF
 - New value of > 450 and ≤ 480 ms
 - New value of > 480 and ≤ 500 ms
 - New value of > 500 ms
 - Increase from Baseline of > 30 ms to ≤ 60 ms
 - Increase from Baseline of > 60 ms
- HR
 - Increase from baseline $> 25\%$ and to a value > 100 bpm
 - Decrease from baseline $> 25\%$ and to a value < 50 bpm
- PR
 - Increase from baseline $> 25\%$ and to a value > 200 ms
 - New value of > 200 ms
- QRS
 - Increase from baseline $> 25\%$ and to a value > 120 ms
 - New values of QRS > 120 ms

A listing of all ECG assessments will be produced by cohort and notable abnormalities will be flagged. In the listing, the assessments collected during the post-treatment period will be flagged. In addition, descriptive statistical analysis (mean and standard deviation) by time point of assessment for Δ QTcF (QTcF change from baseline) will be carried out.

Left ventricular ejection fraction (LVEF) data will be reported on the “Cardiac Imaging” eCRF. The worst decrease in LVEF from baseline will be calculated for each participant (by subtracting the baseline LVEF % from the LVEF % at each post-baseline assessment) and summarized. The summary will include the number and percentage of participants regardless of the method used in the following notable LVEF values:

- Absolute decrease from baseline $\geq 10\% < 20\%$ or LVEF $\geq 40\% \leq 50\%$ (CTCAE grade 2)
- Absolute decrease from baseline $\geq 20\%$ or LVEF $\geq 20\% < 40\%$ (CTCAE grade 3)
- Absolute LVEF $< 20\%$ (CTCAE grade 4)

LVEF shift table to compare baseline to the worst post-baseline on-treatment value (the lowest value corresponds to “worst”) will also be presented.

Baseline categories is defined as follows:

- LVEF > 50%, LVEF \geq 40% \leq 50%, LVEF \geq 20% $<$ 40%, LVEF $<$ 20%

Post-baseline categories correspond to CTCAE grade, defined as follows:

- LVEF > 50%,

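### Time to first AESI is limited to participants who had an AESI, and a date-only baseline lets the 4-hour post-dose C1D1 ECG serve as the QTcF baseline

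*SAP*

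**What the plan says.** **AESI onset (SAP 2.9.1.4).** Time to first AESI, any grade and grade ≥ 3, is to be estimated by Kaplan-Meier, both regardless of relationship and for events suspected to be drug related. For participants without an event the section provides: "In the absence of an event during the on-treatment period, the censoring date applied will be the earliest of the following dates", and lists death, new antineoplastic therapy, end of the on-treatment period, cut-off and consent withdrawal. The next paragraph sets the population: "All participants who experienced at least one AESI in the Safety set will be included in time to first occurrence of AESI"; the same sentence also covers duration. The paragraph after that deals with duration alone, which "will be presented for the subset of subjects in the safety set who experienced the event".

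**Baseline (SAP 2.1.3.7).** For safety and efficacy, "the last available assessment on or before the date of start of study treatment is defined as" baseline. There is no clock-time or pre-dose condition. The same-day rule that follows is for laboratory values only: "If labs with duplicate laboratory measurements taken at the last assessment date on or before the start date of study treatment".

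**ECG schedule and use.** For Cycle 1 Day 1 and Day 15, Protocol Table 8-4 gives "Pre-dose and 4 hours post-dose (within 15 minutes prior to PK". The on-treatment period in SAP 2.1.3.8 runs "from date of first administration of study treatment to 30 days after date of last actual administration of study treatment". SAP 2.9.4.1 tabulates QT/QTcF increases above 30 and above 60 ms, new-value categories and shift tables, and for QTcF change plans a "descriptive statistical analysis (mean and standard deviation) by time point of assessment".

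**The concern.** A Kaplan-Meier estimate of time to onset needs everyone at risk in the denominator. If only participants who had the event are admitted, the curve describes when the event happened among those who had it. It says nothing about how likely it was, yet it will be read as cumulative incidence and will show a finite median onset even for a rare event. The censoring rule one paragraph earlier then has nobody to act on in the any-grade, all-cause analysis of a given AESI.

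The ECG problem is separate but of the same kind. A baseline taken 4 hours after the first dose already contains any acute drug effect, so subtracting it removes that effect from every later change. The C1D1 4-hour record would also be both baseline and on-treatment value, with a change of zero by construction. QTc matters for this drug: Protocol 2.2.3.3.2 reports QTc prolongation in 2 of 39 first-in-human patients, and Table 6-3 has a QTc dose-modification row.

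**Working it through.** The documents give no figure to reproduce on either point. The defects follow from the text; the sizes below rest on assumed inputs.

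**A. AESI onset**

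*Reading the text.* The population sentence covers onset and duration together. Duration then gets its own event-only statement, so the restriction adds nothing for duration and takes effect only on onset. For one AESI, any grade and any cause, all those admitted have the event, so the product-limit estimate ends at 0 and the cumulative curve at 100%. For grade ≥ 3 or drug-related events, or if the sentence means at least one AESI of any type, some admitted participants would be censored. Everyone with no AESI is still left out.

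*Size.* Let c be the crude incidence and S the share still at risk at the end. Under constant hazards the full-set estimate is

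F = 1 − exp[(c/(1 − S)) · ln S].

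- c = 0.20, S = 0.3: (0.20/0.70) × (−1.204) = −0.344, so F = 29.1%. The event-only set gives 100%.
- c = 0.10: F = 12.9% (S = 0.5), 15.8% (S = 0.3), 22.6% (S = 0.1). The event-only set gives 100% each time.
- Grade ≥ 3, if a quarter of AESIs reach it (c = 0.20, S = 0.3): full set 29.1%/4 = 7.3%. Simulation of 4,000 trials of 120 participants gives 7.3% for the full set and 28.1% for the set the SAP states.

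**B. QTcF baseline**

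*Reading the text.* Both C1D1 ECGs carry the date of first dose, and the later of the two is the 4-hour one. Protocol 2.2.3.3.3 puts median Tmax at 3 to 4 hours. After the first dose, Table 8-4 schedules four ECG sets: C1D1 4 h, C1D15 pre-dose, C1D15 4 h and end of treatment. Two of these are 4-hour sets, and the rule turns one of them into baseline. The same-date worst-case rule in SAP 2.1.3.9 does not help: it belongs to the assessment windows, tabulated for ECOG and PRO data. Laboratory values escape because Protocol 8.5.4 has them sampled before dosing.

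*Bias in the mean.* Let E be the mean C1D1 4-hour effect. Change from a post-dose baseline equals change from a pre-dose baseline minus E, so every later mean change is understated by E. If the two C1D1 sets are averaged, it is understated by E/2.

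*Share above 30 ms at C1D15 4 h.* Assume the same E on both days and a normally distributed change with standard deviation SD (the SD of the change itself):

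P = 1 − Φ((30 − m)/SD), with m = E (pre-dose baseline), E/2 (day average) or 0 (post-dose baseline).

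| SD (ms) | Pre-dose baseline, E = 5 / 10 / 15 ms | Day average, E = 5 / 10 / 15 ms | Post-dose baseline |
|---|---|---|---|
| 10 | 0.6 / 2.3 / 6.7% | 0.3 / 0.6 / 1.2% | 0.1% |
| 15 | 4.8 / 9.1 / 15.9% | 3.3 / 4.8 / 6.7% | 2.3% |
| 20 | 10.6 / 15.9 / 22.7% | 8.5 / 10.6 / 13.0% | 6.7% |

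Example: SD 15, E = 10, pre-dose baseline: (30 − 10)/15 = 1.33, giving 9.1%. With the post-dose baseline: 30/15 = 2, giving 2.3%.

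**The case against.** **On AESI.** SAP 2.9 says the Safety Set is used for all safety analyses, and a no-event censoring rule makes sense only for the full set. The restriction may therefore be a drafting slip that a careful programmer would ignore. That is plausible, but the general statement does not override a specific sentence naming who enters this analysis, and the SAP should not depend on the programmer choosing well. It does stand that 100% applies only to the any-grade, all-cause curve of a given AESI, and that the separate count-and-percentage table reports incidence correctly.

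**On the ECG.** The SAP works by date and does not order records within a day, so one could call it silent rather than wrong. Protocol 8.5.3 also speaks of a mean QTc per visit from the triplicates, which could support averaging the day. That halves the bias to E/2 but does not remove it. Neither document states a pre-dose baseline for the ECG analysis.

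**On the protocol's other ECG baselines.** The screening-ECG definition in Table 6-3 governs management of individual participants, and Protocol 8.5.3 refers to pre-treatment baseline in the context of safety monitoring. A summary-table baseline may legitimately differ from these. That stands. The cross-reference requested below is for clarity, and the finding does not depend on it.

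**On size and scope.** The AESI rates, E and SD are all assumed, and if there is no acute QTc effect there is no bias. No hypothesis test, success criterion or futility rule is affected. This limits the severity but is no reason to keep the text.

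**Conclusion.** Both points hold. As written, the AESI onset curves are conditional on having had an AESI. They overstate cumulative incidence: 100% against 29% for any grade, and about 28% against 7% for grade ≥ 3, assuming 20% crude incidence, a quarter of AESIs at grade ≥ 3, 30% still at risk and constant hazards. The date-only baseline allows a post-dose ECG to be the QTcF reference. Mean change is then understated by E (E/2 under a day average), and the increase categories, new-value categories and shift tables are diluted in the reassuring direction whenever E is positive.

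The consequences are confined to descriptive safety outputs. The AESI count table, the ECG listings with flagged values and the expedited review of QTcF above 500 ms are unaffected. The changes should be made, but nothing in the efficacy conclusions turns on them.

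**What to change.** 1. **SAP 2.9.1.4.** Include all Safety Set participants in time to first AESI. Censor those without the event being analysed (that AESI, grade and relationship) by the rule already given. Keep the event subset for duration only.
2. **SAP 2.1.3.7.** Define the ECG analysis baseline as the mean of the last triplicate taken before the time of first dose: C1D1 pre-dose, or screening if that is missing. Use the C1D1 4-hour ECG only as an on-treatment value.
3. **Cross-reference.** State how this analysis baseline relates to the screening-ECG baseline in the QTc row of Protocol Table 6-3, so that the passages are reconciled. This concerns the analysis definition only and leaves the dose-modification rule as it is.

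Cost: two SAP sentences, one cross-reference and minor programming. No new data are needed, but the ECG derivation must use recorded times as well as dates.
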